9.7 Follow-up of Adverse Events

If a participant experiences any clinical or laboratory abnormality attributed to the study drug, they will be monitored until the abnormality returns to baseline (as defined at enrollment) or stabilizes. This procedure is implemented in the study database and case report forms and includes both adverse events and serious adverse events. Participants can take medications for symptomatic relief (e.g. anti-emetics, anti-diarrhea, analgesics).

9.8 Guidelines for Assessing Severity of an Adverse Event

Adverse events will be graded on a scale from 1 to 5 according to the NIH Common Terminology Criteria for Adverse Events (CTCAE), Version 5.0

(https://ctep.cancer.gov/protocoldevelopment/electronic_applications/docs/CTCAE_v5_Quick_Reference_5x7.pdf). A summary is below.

- Grade 1 Mild; asymptomatic or mild symptoms; clinical or diagnostic observations only; intervention not indicated.
- Grade 2 Moderate; minimal, local or noninvasive intervention indicated; limiting age-appropriate instrumental activities of daily living (ADL).
- Grade 3 Severe or medically significant but not immediately life-threatening; hospitalization or prolongation of hospitalization indicated; disabling; limiting self-care ADL.
- Grade 4 Life-threatening consequences; urgent intervention indicated.
- Grade 5 Death related to AE.

9.9 Guidelines for Determining Causality

Attribution of all grade 2 and higher AE's as treatment related or not will be done in two ways. First, attribution will be done by the treating clinician at the time of clinical evaluation using the formal assignment detailed below. Later, attribution will be done again by investigators in aggregate data review and reporting.

Attribution Standards:

1. Unrelated: The AE is *clearly not related* to the investigational agent
2. Unlikely: The AE is *doubtfully related* to the investigational agent
3. Possible: The AE *may be related* to the investigational agent
4. Probable: The AE is *likely related* to the investigational agent

5. Definite: The AE is *clearly related* to the investigational agent

9.10 Serious Adverse Events

Investigators will report to the Primary Investigator (PI) all serious adverse events within 24 hours of becoming aware of the event, regardless of relationship or expectedness.

For serious adverse events, all requested information on the AE/SAE CRF will be provided. However, unavailable details of the event will not delay submission of the known information. As additional details become available, the AE/SAE CRF will be updated and submitted.

9.11 Unexpected Non-serious Adverse Events

An unexpected, non-serious adverse event that is of Grade 2 severity or higher and study related will be recorded and reported to the PI under the serious adverse event reporting procedure above (i.e., within 24 hours).

9.12 Reporting to Health Authority

The Principal Investigator sponsor for the IND will report all AEs and SAEs to the FDA within the reporting time limits set forth by the FDA.

9.12.1 Standard Reporting (IND Annual Report)

This option applies if the AE is classified as one of the following:

- Serious, expected, suspected adverse reactions
- Serious and not a suspected adverse reaction
- Pregnancies

*Note that all adverse events (not just those requiring 24-hour reporting) will be reported in the Annual IND Report.

9.12.2 Expedited Reporting

The investigators must report in an IND safety report any suspected adverse reaction to study drug that is both serious and unexpected. In particular, any cases of anaphylaxis potentially due to the study drug must be reported. The time frame for submitting an IND safety report to FDA and all participating investigators is no later than 15 calendar days after the PI determines that the suspected adverse reaction or other information qualifies for reporting.

Unexpected fatal or life-threatening suspected adverse reactions represent especially important safety information and, therefore, must be reported more rapidly to FDA. The requirement for reporting any unexpected fatal or life-threatening suspected adverse reaction to FDA is no later than 7 calendar days after the sponsor's initial receipt of the information.

Investigators must submit IND and/or CTA safety reports as required by IRB. Documentation of the submission and receipt by the IRB must be retained for each IND safety report.

9.13 Protocol Violations

All protocol deviations will be recorded in a protocol deviation log by qualified study personnel. Based on IRB policies, protocol violations will be reported to the Institutional Review Board within 5 days of the protocol violation. As warranted, the PI will develop a corrective action plan to present to the IRB to address deviations and/or violations.

9.14 Reasons for Early Termination

Study drug administration must be discontinued if any of the following occurs:

- Participant develops grade 3 adverse drug reaction.
- Participant desires to discontinue participation in the study (withdrawal of consent)
- Participant is unwilling or unable to comply with the protocol.
- The investigator feels that is in the participant's best interest to discontinue treatment with study drug.

Participants who halt study drug due to an AE will continue to be followed until AE resolution or stabilization.

9.14.1 Halting the Study

The study will be halted if:

- At any point in the study the Investigators feel that there are safety concerns in this study that put the participants at increased risk as compared to the original information on risk in the consenting process; enrollment will be paused and a safety review will be performed. The investigators in discussion with the FDA can choose to stop the study.

OR

- The independent Data and Safety Monitoring Committee for the study, after reviewing data on a rolling basis concludes that it is in the best interests of the participants to discontinue the study.

Investigators and DSMC will consider the following to guidelines for adverse drug reactions (ARs) to guide decisions regarding study suspension. Given the severity of PH-ILD disease, the DSMC will need to assess the safety data to make final decisions and recommendations, including consultation with IRB and FDA as they deem important.

Grade 2 serious ARs

- If a total of 3 or more grade 2 ARs occur, enrollment will be paused and a safety review performed.

Grade 3 or 4 serious ARs

- If 1 grade 3 or 4 serious AR occurs, enrollment will be paused and a safety review performed.

Grade 5 (fatal)

- Any incidence will lead to pausing enrollment and a safety review.

A final decision to halt the study will be made by the investigators after consultation with the DSMC. Such a decision with its supporting documentation and possible future plans including possible protocol amendments for the study will be submitted to, and discussed with, the FDA.

9.15 Data Safety Monitoring

An independent Data and Safety Monitoring Committee (DSMC) will be established. The DSMC will consist of 3 individuals representing statistical and clinical expertise needed to perform the role of safety oversight and interpretation of data for this trial. Members will be selected to ensure no conflict of interest exists relative to study outcomes and will not be directly engaged in study conduct.

The DSMC will monitor the trial, review safety data, and assess the performance of trial operations and will provide recommendations on whether the trial should continue as planned, be modified, or be stopped. Any action taken by the Board, and the reasons for the action, will be recorded. These documents will include any data summaries or analyses provided to the DSMC and will remain confidential until the study is concluded. The DSMC charter includes additional details on roles and responsibilities.

10 STATISTICAL METHODS AND CONSIDERATIONS

10.1 Analysis Population

There will be two analysis populations for the trial: the intent-to-treat (ITT) and per-protocol (PP) populations. The following description provides how the populations will be derived and analyzed:

- ITT population
 - Composed of all randomized participants
 - Analyzed according to their assigned treatment arm
- PP population
 - Composed of all randomized participants who completed treatment and didn't have any major protocol deviations
 - Analyzed according to their assigned treatment arm

10.2 Descriptive Statistics

Descriptive statistics will be reported for all key participant variables, including, but not limited to,

baseline clinical and demographic characteristics, use of medications, laboratory values, vital signs, clinical outcomes, adverse events, compliance, and study completion status. Proportions will be presented for categorical variables. Continuous variables will be presented using means, standard deviations, and number of observations if the data are normally distributed. If the data are not normally distributed, then continuous variables will be presented using medians and interquartile ranges. In all cases, between-group comparisons will be assessed using absolute standardized differences.

10.3 Analysis of Primary Endpoints

The primary endpoint is the change in PVR on RHC from baseline to the end of treatment period. No hypothesis testing will be performed in analyzing the primary endpoint. The primary endpoint will be analyzed in the ITT population.

The PVR on RHC will be presented as means, standard deviations, number of observations and 95% confidence intervals for each randomization arm. Differences in PVR may be calculated between the treatment group, placebo group, and different types of PH (e.g. Group 1 versus Group 3) to assess treatment differences. The analysis will be performed after all participants in the ITT population have reached the end of treatment or have been withdrawn from the trial.

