10.4 Analysis of Secondary Endpoints

All secondary endpoints will be analyzed in the ITT population.

The proportion of participants experiencing adverse events (AE) events will be summarized by AE type and treatment arm. The proportion of participants experiencing an AE will be calculated as the number of participants who have experienced an AE divided by the number of participants in the ITT population. AEs will be summarized by each arm separately. AEs may be compared by arm using a Fisher's exact test.

The proportion of participants experiencing serious adverse events (SAE) events will be summarized by SAE type and treatment arm. The proportion of participants experiencing an SAE will be calculated as the number of participants who have experienced a SAE divided by the number of participants in the ITT population. SAEs will be summarized by each arm separately. SAEs may be compared by arm using a Fisher's exact test.

The baseline, follow-up, and change from baseline in mPAP, 6MWDT, EMPHAIS-10 score, SGRQ score, serum HA concentration, and NT-proBNP will be summarized using means, standard deviations numbers of observations, and 95% confidence intervals for each randomization arm. Differences in these measures may be calculated between the treatment and placebo group overall and within different types of PH (e.g. Group 1 versus Group 3) to assess treatment differences.

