10.5 Analysis of Exploratory Endpoints

All exploratory endpoints will be analyzed in the ITT population and will be analyzed after all participants have completed treatment or have withdrawn from the trial.

The baseline, follow-up, and change from baseline in inflammatory markers, pro-inflammatory cytokines, PFTs (including FEV1, FVC, TLC, and DLCO), and EBC HA concentration, and HA fragment size will be summarized using means, standard deviations numbers of observations, and 95% confidence intervals for each randomization arm. Differences in these measures may be calculated between the treatment group, placebo group, and different types of PH (e.g. Group 1 versus Group 3) to assess treatment differences. The pharmacokinetics and fragment size will be described. There will also be a sensitivity analysis to investigate whether drug product used (Isochol vs Cantabiline) led to differential primary endpoint outcomes, using a stratified analysis by drug product.

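### Section 10.3 makes the H01-minus-placebo difference in change in PVR optional, with no estimator or confidence interval, and firmly commits only to summaries by arm

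*Combined protocol and SAP*

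**What the plan says.** Section 1.1 gives the primary objective as clinical efficacy over 24 weeks and says that the data will inform larger studies. Sections 1.2 and 4.1 define the primary endpoint as change in PVR, and Section 10.3 repeats it: "The primary endpoint is the change in PVR on RHC from baseline to the end of treatment period". No hypothesis test is planned.

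The firm commitment follows: "The PVR on RHC will be presented as means, standard deviations, number of observations and 95% confidence intervals for each randomization arm". The contrast between arms is permitted but not required: "Differences in PVR may be calculated between the treatment group, placebo group, and different types of PH".

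Other sections bear on the point:
- Section 10.2, which covers clinical outcomes: "In all cases, between-group comparisons will be assessed using absolute standardized differences".
- Section 10.4 names all three quantities for secondary endpoints ("The baseline, follow-up, and change from baseline in mPAP", and so on), as does Section 10.5 ("The baseline, follow-up, and change from baseline in inflammatory markers", and so on). Section 10.3 does not do so for PVR.
- Section 10.4 also leaves the difference optional, but words the PH-type results as treatment-placebo differences within type: "Differences in these measures may be calculated between the treatment and placebo group overall and within different types of PH".
- Section 10.5 is firm about a secondary check on the primary endpoint: "There will also be a sensitivity analysis to investigate whether drug product used (Isochol vs Cantabiline) led to differential primary endpoint outcomes".
- Section 10.7 gives 16 participants, 5:3 allocation and stratification by PH type, with no power basis.
- Section 11.2 lists a statistical analysis plan in the trial master file. No separate text of it was supplied.

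**The concern.** A placebo group is there to supply the difference between arms. Here that difference is the one part of the primary analysis that may be left out, while a check on the primary result by drug product is promised. If the difference is calculated, its form can be chosen after unblinding: simple difference in mean change or baseline-adjusted difference, with or without the stratum, with or without a CI. In a trial of 16, that choice and a chance imbalance in baseline PVR can both move the headline figure.

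Two smaller defects sit alongside. The phrase used for the firm summary does not say whether it means PVR level or change. Sections 10.3 and 10.5 also offer a comparison of Group 1 with Group 3 as a way to assess treatment differences. PH type is not randomised, so that comparison is not a treatment effect.

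**Working it through.** **Inputs from the documents.** 16 × 5/8 = 10 on H01 and 16 × 3/8 = 6 on placebo (Section 10.7). Entry requires PVR of at least 400 dyn·s·cm⁻⁵ (Section 5.1). No SD, effect size or correlation is given, so there is no planned figure to reproduce.

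**Assumptions.** Baseline PVR is normal with mean 550 and SD 225 before truncation at 400, so enrolled patients have mean about 646 and SD about 164. The baseline-to-Week 24 correlation r (before truncation) is 0.5, 0.7, 0.8 or 0.9. There are 5:3 participants in each of two strata, and PH type has no effect on change. Below, SD means the pre-truncation SD of 225.

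**1. Does the committed between-group measure fill the gap?** With no drug effect, the absolute standardized difference equals |t₁₄| × √(1/10 + 1/6) = |t₁₄| × 0.516.
- Mean: 0.844 × 0.516 = 0.436.
- Chance of exceeding 0.5: P(|t₁₄| > 0.5/0.516) = P(|t₁₄| > 0.968) = 0.35.

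It is sizeable by chance alone and does not show which arm did better.

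**2. Can a reader recover the effect?** If the summary by arm is of change, yes: difference in means ± 2.145 × pooled SD × 0.516, that is ± 1.11 SD of the change score. This gives the unadjusted difference only.

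**3. What does the open choice of estimator allow?** Simulation of 60,000 trials per value of r. Week 24 = r × baseline + √(1 − r²) × normal error, in SD units. The two estimators are the difference in mean change, and a linear model for change with baseline PVR and PH type. Rows are with no drug effect unless stated.

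| | r = 0.5 | 0.7 | 0.8 | 0.9 |
|---|---|---|---|---|
| Mean apparent benefit if the better is always taken, SD | 0.078 | 0.055 | 0.038 | 0.024 |
| The same × 225, dyn·s·cm⁻⁵ | 18 | 12 | 9 | 5 |
| Trials in which the two differ in sign | 13% | 11% | 10% | 8% |
| Median size of the change estimate in those trials, SD | 0.12 | 0.08 | 0.06 | 0.04 |
| 95% half-width, change, SD | 1.02 | 0.81 | 0.67 | 0.48 |
| 95% half-width, model, SD | 0.99 | 0.82 | 0.69 | 0.50 |
| Sign disagreement with a true effect of 0.5 SD | 8% | 5% | 3% | 1% |

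Where the two differ in sign, the estimates are about a tenth of the half-width.

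**4. Baseline imbalance.** The arm means at baseline differ by more than 0.5 SD (0.5 × 225 = 112 dyn·s·cm⁻⁵) in about 18% of trials. The range is 15 to 22% for pre-truncation means of 500 to 600 and SDs of 200 to 250. An imbalance of 0.5 SD shifts the expected unadjusted difference in change by (r − 1) × 0.5: 0.25, 0.15, 0.10 and 0.05 SD in size. The adjusted estimate removes this shift under the linear model.

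**5. Precision.** With 16 completers, the model's interval is 3% narrower at r = 0.5 and then 1, 3 and 4% wider. With 13 completers (8 and 5) it is equal, then 4, 6 and 7% wider. The two covariates cost two residual degrees of freedom (t of 2.179 against 2.145).

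**The case against.** The strongest reply is that this is a 16-patient Phase 2a trial that declares no hypothesis test and no power basis, so descriptive reporting by arm is a stated choice. That limits the consequence, and the absence of a test is not a defect. But an estimate with a CI needs no test, and the plan already promises CIs by arm.

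Four stronger readings may tempt a reader, and the documents do not support them.
- *The firm summary is of PVR levels, so the CI of the effect could never be recovered.* That CI would indeed need the unreported correlation. But Sections 1.2, 4.1 and 10.3 all define the endpoint as change, and the summary most naturally refers back to that definition. The wording needs clarifying and no more.
- *The open choice can reverse the result in a quarter to a third or more of trials, or create about 0.15 SD of benefit.* Such figures (25 to 37% sign disagreement) arise only if raw Week 24 PVR is a candidate, and it is not the declared endpoint.
- *Adjustment is needed for precision.* By step 5 it gains little or loses slightly. The case for it is baseline imbalance and advance choice, and preferring the model to the simple difference is partly judgement.
- *No estimator has been fixed anywhere.* Section 11.2 lists an analysis plan that may contain one. The statement holds only for the text supplied.

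What remains is that the contrast which answers the primary objective is optional and undefined in this text.

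**Conclusion.** The point holds and should be fixed, although the trial stays interpretable without it. In the documents supplied, the only firm between-group measure is unsigned and has no stated CI, and the signed difference in change in PVR is neither required nor defined.

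The size is modest. Open choice between change and adjusted change is worth on average at most about 0.08 SD (18 dyn·s·cm⁻⁵), and that assumes the better result is always picked. Sign disagreement, in about 8 to 13% of trials with no effect, is confined to estimates near zero. Baseline imbalance matters more: in roughly one trial in five or six it is large enough to shift the unadjusted difference by 0.05 to 0.25 SD or more. All of these figures rest on the assumed SD, correlations and truncated baseline. The 0.44 and 35% for the standardized difference rest only on 10 against 6 and approximate normality. The textual finding needs no assumption.

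**What to change.** In Section 10.3, write:

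*Baseline, Week 24 and change in PVR will be tabulated by arm. The H01-minus-placebo difference in change in PVR will be reported with a two-sided 95% CI and no hypothesis test, from a linear model with baseline PVR and PH type (randomisation stratum) as covariates; the unadjusted difference in mean change with its 95% CI will be reported alongside. For efficacy endpoints these estimates take precedence over the absolute standardized difference in Section 10.2. Results by PH type are H01-minus-placebo differences within Group 1 and within Group 3, descriptive only.*

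In Section 10.4, make the difference mandatory, with a 95% CI. In Section 10.5, use the same within-PH-type wording. If a separate analysis plan already fixes the estimator, refer to it in Section 10.3.

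The essential part is one signed difference in change with its CI, fixed before unblinding.

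The cost is wording and one small regression, with no extra patients, visits or data. Under the assumptions above, the adjusted interval may be up to about 4% wider than the unadjusted one with 16 completers and 7% wider with 13, which is why both are reported.

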9	MONITORING AND REPORTING OF ADVERSE EVENTS	25
9.1	Adverse Events Definition.....	25
9.2	Suspected Adverse Reaction Definition	25
9.3	Serious Adverse Event or Serious Adverse Reaction Definition.....	25
9.4	Unexpected Adverse Event or Reaction Definition.....	25
9.5	New Fact	26
9.6	Identification of Adverse Events	26
9.7	Follow-up of Adverse Events	27
9.8	Guidelines for Assessing Severity of an Adverse Event.....	27
9.9	Guidelines for Determining Causality	27
9.10	Serious Adverse Events	28
9.11	Unexpected Non-serious Adverse Events.....	28
9.12	Reporting to Health Authority	28
9.12.1	Standard Reporting (IND Annual Report).....	28
9.12.2	Expedited Reporting	28
9.13	Protocol Violations	29
9.14	Reasons for Early Termination	29
9.14.1	Halting the Study	29
9.15	Data Safety Monitoring.....	30
10	STATISTICAL METHODS AND CONSIDERATIONS.....	30
10.1	Analysis Population	30

The SATURN Study [CONFIDENTIAL – DO NOT REDISTRIBUTE]

10.2	Descriptive Statistics.....	30
10.3	Analysis of Primary Endpoints	31
10.4	Analysis of Secondary Endpoints	31
10.5	Analysis of Exploratory Endpoints	31
10.6	Missing Data Handling	32
10.7	Sample Size and Randomization	32
11	DATA COLLECTION, RETENTION AND MONITORING	32
11.1	Data Collection Instruments	32
11.2	Data Management Procedures	33
11.3	Data Quality Control and Reporting.....	33
11.4	Archival of Data.....	33
11.5	Availability and Retention of Investigational Records	34
11.6	Subject Confidentiality	34
12	ETHICAL CONSIDERATIONS	34
12.1	IRB and HIPAA.....	34
12.2	Potential Participant Risks	36
12.3	Potential Benefits	36
13	Abbreviations	36
14	References.....	37

1 **BACKGROUND**

1.1 **Introduction**

This is a prospective, randomized, double-blind, study of H01 of 24 weeks in adults with pulmonary hypertension (PH) with an optional open-label extension (extension to 48 weeks). The primary objective of this double-blinded study is to evaluate the clinical efficacy of H01 over 24 weeks. Secondary objectives are to investigate the safety and tolerability of H01 and pharmacokinetic (PK) and pharmacodynamic (PD) markers in this population. Following IRB approval and written informed consent, a total of 16 participants will be enrolled, randomized approximately 2:1 (H01 1600 mg/day : placebo), stratified by PH type, and treated for 24 weeks. Data from this study will inform future larger studies. Participants will have the opportunity to extend their participation an additional 24 weeks by consenting to an open-label extension.

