1.3 Scientific Rationale

1.3.1 *Urgent need for pulmonary hypertension therapeutics*

Pulmonary hypertension (PH) is defined by a pulmonary vascular resistance (PVR) ≥ 3 WU associated with an increased mean pulmonary arterial pressure (mPAP >20 mmHg) at rest¹. It can lead to right ventricle hypertrophy (RVH), right-sided heart failure and eventually death^{7,10}. Idiopathic pulmonary fibrosis (IPF) is a form of restrictive interstitial lung disease (ILD) associated with extremely poor outcomes. IPF is characterized by parenchymal fibrosis that leads to impaired gas exchange⁸. PH, with a prevalence of about 40% in advanced disease^{9,10}, is a common complication in IPF where it is strongly associated with increased morbidity and mortality^{10,11}. It is classified as WHO Group 3 PH¹².

There are limited treatment options for patients with interstitial lung disease and PH, with lung transplantation being the only “curative” option. Despite the many pharmacological agents available to treat pulmonary arterial hypertension (PAH) (classified as Group 1 PH, where no lung parenchymal component is observed), these agents have been shown to be either ineffective or detrimental to patients with IPF + PH¹³. Consequently, it is essential to develop improved medical therapies for IPF+PH.

1.3.2 *Discussion on pulmonary hypertension groups*

This trial selects patients from Groups 1 and 3 PH based on the hypothesized utility of H01 in PH due to lung conditions associated with inflammation, vascular remodeling, and fibrosis. Brief discussion of these groups provides relevant context for selected inclusion/exclusion criteria.

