8 STUDY DRUG PROCEDURES

8.1 Treatment Assignment

Up to 16 eligible participants will be randomly assigned to H01 or placebo in a 5:3 ratio using a computer-generated randomization scheme, stratified by PH type, developed by an unblinded biostatistician at Stanford University. The code used to generate the allocation, along with the seed used in the random number generation, will be stored on secure servers and maintained by the unblinded biostatistician.

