10.7 Sample Size and Randomization

A total of 16 participants with PH will be enrolled in the study. Participants will be randomized 5:3 to treatment:placebo. Randomization will be stratified by PH type. As no formal hypothesis testing will be performed on the primary endpoint, this sample size is not based on a statistical powering. However, data on hand regarding clinical improvement and HA changes in preclinical and clinical settings suggests we will be able to draw meaningful insights from a study of this size that informs future trials.

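### PH type stratifies the randomisation but enters no committed analysis, and the optional wording in 10.3 and 10.5 lists a Group 1 versus Group 3 difference as a way to assess treatment

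*Combined protocol and SAP*

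**What the plan says.** - **Design.** Section 8.1 has assignment "stratified by PH type", and 10.7 repeats this. On size, 10.7 states: "A total of 16 participants with PH will be enrolled in the study" and "Participants will be randomized 5:3 to treatment:placebo". The size of each stratum is not given.
- **Firm analyses.** Sections 10.3, 10.4 and 10.5 commit to means, SDs, counts and 95% confidence intervals for each randomisation arm, and 10.4 commits to AE and SAE proportions by arm. The one firm stratified analysis, in 10.5, splits the primary endpoint by drug product.
- **Optional use of PH type, PVR (10.3).** "Differences in PVR may be calculated between the treatment group, placebo group, and different types of PH (e.g. Group 1 versus Group 3"; the stated purpose is to judge how treatment differs.
- **Optional use, PFTs and biomarkers (10.5).** "Differences in these measures may be calculated between the treatment group, placebo group, and different types of PH (e.g. Group 1 versus Group 3", with the same purpose.
- **Optional use, secondary endpoints including SGRQ (10.4).** Differences may be taken "between the treatment and placebo group overall and within different types of PH".
- **Missing data (10.6).** Complete cases only.

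**The concern.** Two things look wrong. First, the factor judged important enough to stratify a 16-person randomisation is absent from every committed table and estimate. Second, the sentence governing the primary endpoint and the lung-function measures puts PH types in the same list as treatment and placebo, as things to be differenced in order to assess treatment. Section 10.4 describes a different comparison, H01 against placebo within type. The three sections therefore do not define the same contrast.

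The types may well differ on these measures. Section 1.3.1 describes PAH as "classified as Group 1 PH, where no lung parenchymal component is observed", while Group 3 in this trial means interstitial lung disease. At stake are a between-disease difference being reported as a treatment finding, a needlessly imprecise overall estimate, and an overall estimate that moves if the strata become unbalanced.

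**Working it through.** **Inputs from the protocol.** N = 16 at 5:3 gives 16 × 5/8 = 10 on H01 and 16 × 3/8 = 6 on placebo. Section 1.1 instead says "randomized approximately 2:1 (H01 1600 mg/day : placebo), stratified by PH type", which would be about 10.7 and 5.3; this does not alter the argument. There is no power calculation to reproduce: 10.7 says the size is not based on power, and no SD, effect size or dropout rate is given.

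**Assumptions, not in the documents.** 8 participants per type, so 5 H01 and 3 placebo in each. Results are in units of the within-type SD of the change. D is the difference between type means.

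**1. What a Group 1 minus Group 3 difference measures.** Five-eighths of each type receive H01.
- No H01 effect, D = 1: Group 1 minus Group 3 = 1.0; H01 minus placebo = 0.
- H01 effect of −1 in both types, D = 0: Group 1 minus Group 3 = 0; H01 minus placebo = −1.
- H01 effect of −1 in Group 3 only, D = 0: Group 1 minus Group 3 = 0 − (5/8 × −1) = 0.625; H01 minus placebo = −0.5.

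The type contrast can be large when the drug does nothing and zero when it works equally in both types.

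**2. Precision of H01 minus placebo.** Half-width = t(0.975, df) × √(1/10 + 1/6), with √(1/10 + 1/6) = 0.516.
- Adjusted for type, df 13: 1.12.
- Unadjusted, df 14, D = 0: 1.11.
- Unadjusted, D > 0: multiply 1.11 by √(1 + 0.25 D²), because the type difference enters the arm SD. This gives 1.14 at D = 0.5, 1.24 at D = 1, 1.38 at D = 1.5 and 1.57 at D = 2.

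The same inflation of the SD (about 1.12 at D = 1, 1.41 at D = 2) affects the intervals for arm means, which are the firm output.

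**3. Imbalance.** With no H01 effect, Group 1 mean 1 and Group 3 mean 0, the unadjusted contrast is the Group 1 share in the H01 arm minus the Group 1 share in the placebo arm.
- 5:3 and 5:3: 5/10 − 3/6 = 0.
- 6:2 in Group 1 and 4:4 in Group 3: 6/10 − 2/6 = 0.27.
- Two Group 1 placebo participants lost from a 5:3 and 5:3 start, complete cases: 5/10 − 1/4 = 0.25.

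**4. Precision within a type.** Half-width = t(0.975, n1 + n2 − 2) × √(1/n1 + 1/n2): 1.79 for 5 v 3, 1.49 for 6 v 4, 2.40 for 4 v 2, 2.91 for 3 v 2.

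**The case against.** The best reply is that 10.3 and 10.5 are only loosely drafted. Their sentence also names treatment and placebo, so H01 versus placebo is among the permitted contrasts. The same Group 1 and Group 3 parenthesis appears in 10.4 straight after the reference to comparisons within types, where it merely names the types. A non-randomised comparison may never have been intended. That is a fair reading, but it supports correcting the sentence: the clear wording sits with the secondary endpoints and the ambiguous wording with the primary one.

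It can also be said that this is a descriptive 16-person study with no test of the primary endpoint, and that within-type estimates are too imprecise to act on. This stands, and it is why those rows should be descriptive only. It does not bear on stratifying the overall estimate.

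Several stronger readings are tempting and are not supported:
- **That the type contrast says nothing about H01.** It carries interaction (0.625 in the third case above). It just cannot separate that from disease type.
- **That pooling is biased.** With balanced strata it estimates an average effect.
- **That SGRQ has no within-type comparison.** Section 10.4 covers SGRQ and allows one, though only optionally.
- **That an effect on lung function must be diluted by Group 1 participants.** If H01 changed FVC by d in Group 3 and not at all in Group 1, the pooled H01-arm change would be 0.25d, 0.50d or 0.75d at assumed Group 3 shares of 25%, 50% or 75%. The documents do not say the Group 1 effect is nil: 1.3.2 discusses Group 1 patients with lung disease, and connective tissue disease, which 1.3.3 links to ILD, is an eligible Group 1 cause in 5.1.
- **That the trial is meant to choose a PH type.** Sections 1.1 and 10.7 say only that it will inform later studies.

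**Conclusion.** The point holds as a gap and an inconsistency in the analysis text. No committed analysis uses the stratification factor, and 10.3 and 10.5 permit, under the label of assessing treatment, a contrast that cannot isolate the H01 effect and that conflicts with 10.4.

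The size depends on how far the types differ, which the documents do not give. At a 0.5 SD difference the precision cost of ignoring type is negligible (1.14 against 1.12). At 1 and 2 SD the half-width is about 1.24 and 1.57 against 1.12. If the types do not differ, adjusting costs almost nothing (1.12 against 1.11). Imbalance of the kind shown moves the unadjusted contrast by about a quarter of an SD at a 1 SD type difference. All these figures assume 16 participants at 5:3; the half-widths for the overall contrast also assume equal strata and a common within-type SD.

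**What to change.** - In 10.3 and 10.5, define the difference as *between H01 and placebo, overall (stratified by PH type) and within each PH type*.
- Apply the same stratified overall estimate to the continuous endpoints in 10.4.
- Commit to descriptive rows by arm within PH type for PVR and the PFT measures.
- State that a Group 1 versus Group 3 difference will not be read as a treatment effect.

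The cost is a few words and some extra table rows; no new data are needed. The drawback is small cells, about 5 versus 3 if the types split 8 and 8, with a half-width near 1.8 SD, and wider in the smaller stratum if the split is unequal. Label those rows descriptive.
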